### 5.5.1 Treatment Arms

Subjects will be centrally randomized to one of 7 treatment sequences to receive lasmiditan 50 mg (L50 mg), lasmiditan 100 mg (L100 mg) or lasmiditan 200 mg (L200 mg) or placebo (P) for the initial dose (in a 1:1:1:1 ratio) and the second dose, if needed for rescue or recurrence of migraine as follows:

First dose for treatment of migraine	Second dose for rescue or recurrence of migraine (if needed)
L50 mg	L 50 mg
	L 50 mg
	placebo
L100 mg	L100 mg
	L100 mg
	placebo
L200 mg	L200 mg
	L200 mg
	placebo
placebo	placebo

### 5.5.2 Schedule of Assessments

- **Screening/Visit 1:** The screening examinations to determine subject eligibility are performed. Subjects are randomized and provided with a dosing card.
- **Telephone call, confirmation of eligibility:** Within 7 days after screening, a telephone contact must be made between the site study staff and subject to confirm study eligibility based on clinical laboratory results. If a subject is considered not eligible, he/she will be advised not to take the study drug. An appointment for a follow-up visit (**EoS/Visit 2**) and collection of study drug and diary will be scheduled.
- **EoS/Visit 2: The end of study visit**
  - The subject will return to the clinic for post-treatment follow-up one week (7 days) after a subject completes treatment (treats one migraine attack within 8 weeks)
  - If a subject has not treated a migraine attack within 8 weeks after **Screening/Visit 1** the subject will be contacted to return to the clinic. In this case, this visit will only be used to return the study drug and e-diary.

The overall Schedule of Assessments for the study is provided in Table 1.

## 5.6 Assessments by Study Visit

### 5.6.1 Screening Visit /Visit 1

The following items must be completed and reviewed by the Investigator or sub-Investigator within 14 days:

- Explain the purpose of the study to prospective subjects and obtain written informed consent and HIPAA.
- Document migraine characteristics per IHS criteria (See [Appendix 2](#)).
- Review inclusion/exclusion criteria (See [Sections 6.1](#) and [6.2](#)).
- Document medical history including migraine history and prior treatment and collect demographic information (See [Section 9.1.1](#)).
- Have subject complete MIDAS (See [Section 9.1.1.2](#) and [Appendix 3](#)).
- Record concomitant medications that the subject is taking.
- Document resource utilization (See [Section 9.1.1.3](#)).
- Perform a complete physical examination (including height, weight, and vital signs) (See [Sections 9.1.2](#) and [9.1.3](#)).
- Perform a 12-lead ECG (see [Section 9.1.4](#)).
- Collect blood and urine samples for clinical laboratory tests (hematology, chemistry, and urinalysis; see [Section 9.1.5](#)). The laboratory tests will include serum  $\beta$ HCG for women of childbearing potential (WOCBP). Any woman with a positive pregnancy test will be ineligible for the study. Have subject complete C-SSRS (See [Section 9.1.6](#) and [Appendix 4](#)).
- Review study requirements and instructions on dosing and completing electronic diary (See [Section 9.1.7](#) and [9.1.8](#)).
- Randomize subject through the Interactive Response Technology (IRT) system.
  - For subjects who meet initial screening criteria and are randomized, advise as to when to expect the confirmatory telephone call. Remind subject not to treat a migraine attack with study drug prior to this call.
- Dispense study drug as assigned.
- Provide access to electronic diary.
  - Starting at **Visit 1** and continuing to **EoS/Visit 2**, subjects will be asked daily, how they are feeling and about the use of any concomitant medications.
- Confirm timing of **EoS/Visit 2**.
- Discharge subject.
- A subject may be rescreened only once.

### 5.6.2 Phone Call

Within 7 days after screening, a phone contact must be made between site study staff and subject to confirm study eligibility based on the clinical laboratory results.

- If a subject is eligible, a review of study requirements will be performed. Subjects will update their status in the e-diary to allow them to report a migraine and record dosing and post-dose assessments. Each subject will be reminded of when to treat a migraine attack with study drug, the use of rescue medication, the treatment of recurrence and diary completion along with the need to return to the clinic for **EoS/Visit 2**. Subjects will be asked to treat their next migraine attack providing headache severity is at least moderate and not improving.

- If a subject is considered not eligible, she/he will be instructed not to take the study drug and an appointment to return the study drug and diary must be scheduled and should occur within one week (7 days).

### 5.6.3 Treatment

Subjects will be allowed up to 8 weeks to treat an acute migraine attack of moderate or severe intensity that is not improving. The attack is to be treated within 4 hours of onset.

- **Prior to dosing the subject will record:**
  - Time of onset
  - Time migraine pain becomes moderate or severe and the severity ((2) moderate or (3) severe) of the pain.
  - Presence or absence (yes or no) of each of the following associated symptoms of migraine: nausea, phonophobia and photophobia.
    - From the list of associated symptoms **present** the subject will identify which **ONE** is most bothersome to them as the MBS.
  - Presence or absence (yes or no) of vomiting.
  - Degree of interference with normal activities
- **Subject will dose with study drug and record time of dosing.**
- Subject will record their response to treatment for 48 hours after dosing with study drug. Total time to record response is up to 72 hours (See [Section 9.1.8](#)).
- Subjects will be asked about any adverse events (if they are feeling anything unusual) and about the use of any concomitant medications.

### 5.6.4 End of Study/Visit 2

The following assessments will be performed:

- Collect any unused study drug and review dosing compliance.
- Collect resource utilization (See [Section 9.1.1.3](#)).
- Collect information on missed days of work and/or school due to migraine.
- Have subject complete C-SSRS (See [Section 9.1.6](#) and [Appendix 5](#)).
- Review any information reported since **Visit 1** regarding AEs and use of concomitant medication and confirm/assess for AEs and use of concomitant medications not already reported.
- Perform a brief symptom-related physical examination if indicated by an AE (See [Section 9.1.2](#)).
- Obtain vital sign readings (See [Section 9.1.3](#)).
- Perform a 12-lead ECG (See [Section 9.1.4](#)).
- Collect blood and urine samples for clinical laboratory tests (hematology, chemistry, and urinalysis) (See [Section 9.1.5](#)). The laboratory tests will include a urine pregnancy test for WOCBP. A positive urine pregnancy test will be confirmed with a serum  $\beta$ HCG test. (The confirmatory test may be run in the local clinical laboratory).
- Subject's participation in study is complete.

## 6. SELECTION AND WITHDRAWAL OF SUBJECTS

### 6.1 Inclusion Criteria

All subjects entered into this trial must meet the following criteria:

1. Able and willing to give written informed consent and authorize HIPAA.
2. Patients with migraine with or without aura fulfilling the IHS diagnostic criteria 1.1 and 1.2.1 (ICHD-2004, [Appendix 2](#)).
3. History of disabling migraine for at least 1 year.
4. MIDAS score  $\geq 11$  ([Appendix 3](#)).
5. Migraine onset before the age of 50 years.
6. History of 3 – 8 migraine attacks per month ( $< 15$  headache days per month).
7. Male or female, aged 18 years or above.
8. Females of child-bearing potential must be using or willing to use a highly effective form of contraception (e.g. combined oral contraceptive, IUD, abstinence, or vasectomized partner).
9. Able and willing to complete an electronic diary to record details of the migraine attack treated with study drug.

### 6.2 Exclusion Criteria

Subjects will be excluded from this trial if they meet any of the following criteria:

1. Any medical condition or clinical laboratory test which in the judgment of the Investigator makes the subject unsuitable for the study.
2. Pregnant or breast-feeding women.
3. Women of child-bearing potential not using or not willing to use highly effective contraception.
4. Known hypersensitivity to lasmiditan, or to any excipient of lasmiditan oral tablets, or any sensitivity to a ditan.
5. History or evidence of hemorrhagic stroke, epilepsy or any other condition placing the subject at increased risk of seizures.
6. History of recurrent dizziness and/or vertigo including BPPV, Meniere's disease, vestibular migraine, and other vestibular disorders.
7. History of diabetes mellitus with complications (diabetic retinopathy, nephropathy or neuropathy).
8. History within the previous three years or current evidence of abuse of any drug, prescription or illicit, or alcohol.
9. History of orthostatic hypotension with syncope.
10. Significant renal or hepatic impairment.
11. Subject is at imminent risk of suicide (positive response to question 4 or 5 on the C-SSRS) or had a suicide attempt within six months prior to the screening visit.
12. Previous participation in this clinical trial.
13. Participation in any clinical trial of an experimental drug or device in the previous 30 days.
14. Known Hepatitis B or C or HIV infection.
15. History, within past 12 months, of chronic migraine or other forms of primary or secondary chronic headache disorder (e.g. hemicranias continua, medication overuse headache [[Appendix 2](#)]) where headache frequency is  $\geq 15$  headache days per month.
16. Use of more than 3 doses per month of either opiates or barbiturates.
17. Initiation of or a change in concomitant medication to reduce the frequency of migraine

- episodes within three (3) months prior to **Screening/Visit 1**.
18. Subjects who are employees of the sponsor.
  19. Relatives of, or staff directly reporting to, the Investigator.

Subjects with test results which do not meet the above inclusion/exclusion criteria may have the underlying test repeated once if it is thought to represent a laboratory error, a reversible, clinically insignificant intermittent condition, or is not consistent with the subject's historical values. If inclusion/exclusion criteria are not met after the repeat test, the subject should not be enrolled in the study.

### 6.3 Protocol Exceptions and Deviations

Exceptions to the above eligibility criteria will not be granted. It is expected that subjects will meet all eligibility criteria. Departures from the protocol should be avoided, unless required for the safety of the subject. Protocol deviations will be documented by the study monitor and will be included in the final clinical study report. Protocol deviations should be submitted to the Institutional Review Board (IRB)/Ethics Committee (EC), in accordance with the site's IRB/EC requirements.

### 6.4 Subject Withdrawal Criteria

Subjects may voluntarily withdraw from the study, or be removed from the study at the discretion of the Investigator or Sponsor, at any time. The Investigator may withdraw a subject at any time if it is determined that continuing in the study would result in a significant safety risk to the subject.

If such withdrawal occurs, or if the subject fails to return for **EoS/Visit 2**, the Investigator should determine the primary reason for a subject's premature withdrawal from the study and record the reason in the subject's study records.

Premature withdrawal may occur for any of the following reasons:

- Non-compliance with the protocol requirements
- Pregnancy
- Death
- Adverse event (AE)
- Subject request
- Investigator request
- Sponsor request

For subjects who are lost to follow-up (i.e., those subjects whose status is unclear because they fail to appear for study visits without stating an intention to withdraw), the Investigator should show "due diligence" by documenting in the source documents all steps taken to contact the subject, e.g., dates of telephone calls, registered letters, etc.

All subjects prematurely discontinuing from the trial (prior to **EoS/Visit 2**), regardless of cause, must be seen for **EoS/Visit 2**. Subjects that withdraw from the study prior to dosing a single attack should return to the clinic for **EoS/Visit 2** to return all unused study drug and the e-diary. Subjects who are withdrawn from the study for any reason will not be replaced.

## **7. TREATMENT OF SUBJECTS**

### **7.1 Subject numbering and enrollment status**

At screening, each subject will be assigned a unique seven-digit subject number. The first three characters will be numbers that identify the study site, and will be assigned by the Sponsor. The remaining four characters identify the subject. The latter four numbers will be assigned by the study site personnel in ascending sequential order to each unique subject screened at that site. For example, the subject number for the first subject screened at Study Site 001 would be 001-2001. If a subject is rescreened, the reason for rescreening will be noted and the subject will keep the same number assigned at initial screening. If a subject fails to be randomized, the reason for not being randomized should be documented in the source documents. The subject will be considered a screen failure. If a subject is randomized but is then deemed ineligible at the telephone confirmation the subject will be considered a randomization failure. This subject will return to the clinic to be discontinued. Study drug and the patient e-diary will be collected. A subject deemed to be a randomization failure may be rescreened if the reason for ineligibility is thought to represent a laboratory error, a reversible, clinically insignificant intermittent condition, or is not consistent with the subject's historical values. The subject will be given a new screening number. In this case the subject should not be re-randomized until eligibility is confirmed. If the subject is not re-randomized he/she will be considered a screen failure.

### **7.2 Description of Study Drug**

For study purposes lasmiditan and matching placebo are all referred to as study drug.

### **7.3 Concomitant Medications**

Concomitant medications (including devices), for migraine or pain during the 90 days (3 months) prior to study enrollment and concomitant medication used to treat other medical conditions during the 30 days (1 month) prior to study enrollment will be recorded during **Screening/Visit 1**.

Any changes in dosage or new medications added as a result of intercurrent illness during the subject's time on study must be recorded in the CRFs.

#### **7.3.1 Rescue Medication**

Rescue medication will be permitted after completion of the 2 hour assessments if the migraine does not respond (subject is not headache pain free). If the migraine does not respond within 2 hours a second dose of randomized study drug may be taken up to 24 hours after the first dose as long as no other rescue medication has been used. The Investigator may advise each subject as to an alternative suitable rescue medication. Triptans, ergots, opioids and barbiturates **MUST NOT** be used for rescue medication within 24 hours of study drug administration. The use of rescue medication will be recorded in the subject diary.

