#### **7.3.2 Recurrence Medication**

If the migraine responds within 2 hours (headache becomes pain free) but then recurs after 2 hours, a second dose of randomized study drug may be taken up to 24 hours after the first dose.

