### 10.3.2 Second Dose Analysis Populations

The analysis populations for the second dose used for rescue or for recurrence will be as defined below. Subjects **must** have taken the second dose and have been considered evaluable for the first dose and primary analysis to be included in the second dose analysis.

**Safety population** All randomized subjects who were considered in the safety population after the first dose and used a second dose of study drug, regardless of whether or not they undergo any study assessments. Subjects are evaluated by the drug they receive, not by the drug to which they are randomized.

**ITT-2nd Dose population** All randomized subjects who were considered ITT after the first dose and used a second dose of study drug and have any post-dose assessments. Subjects are evaluated by the drug to which they are randomized.

**mITT-2nd Dose population** All randomized subjects who were considered mITT after the first dose and used a second dose of study drug and have any post-second dose assessments. Subjects are evaluated by the drug to which they are randomized.

**PP-2nd Dose population** All ITT subjects will be considered per protocol (PP) if they use a second dose for rescue or recurrence of a migraine attack and do not deviate from the protocol.

The 2nd dose ITT, mITT and PP analysis populations will be further qualified by reason for second dose. Subjects will be considered in the 2nd dose rescue populations or 2nd dose recurrence populations as defined:

- **Rescue population:** All randomized subjects who did not achieve headache pain free at 2 hours, completed the 2 hour assessments and took a second dose of study drug between 2 hours and 24 hours.

- **Recurrence population:** All randomized subjects who achieved headache pain free at 2 hours, but then experienced recurrence of mild, moderate or severe migraine pain and took a second dose of study drug up to 24 hours from the first dose.

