##### **10.6.1 Analysis of second dose for rescue**

A second dose of study drug will be considered rescue medication if taken by a subject that did not achieve headache pain free at 2 hours and completed the 2 hour assessments prior to taking the second dose.

Summary statistics will be presented by treatment sequence on relief of migraine symptoms (pain free and MBS free) along with the time course to headache relief explored up to 48 hours. Subjects that use an alternative rescue medication will not be included in the summary statistics of response to treatment for rescue.

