2 SUMMARY OF THE CLINICAL TRIAL PROTOCOL

2.1 Study Summary

This is a prospective, randomized, double-blind, placebo-controlled study in subjects with disabling migraine (MIDAS score ≥ 11). Approximately 2968 subjects will be screened and randomized (742 per treatment group based on the first dose) to ensure that approximately 2280 subjects (570 per treatment group based on the first dose) treat a migraine attack and complete the Treatment Period.

[figure not shown]
Subjects will be asked to treat a migraine attack with study drug on an outpatient basis. Subjects will be provided with a dosing card containing a dose for initial treatment and a second dose to be used for rescue or recurrence of migraine. Each dose consists of two tablets. Each subject's study participation will consist of a screening visit (Visit 1) with a telephone contact within 7 days to confirm eligibility, a Treatment Period of up to 8 weeks, and an EoS visit (Visit 2) within one week (7 days) of treating a migraine attack. The total time on study will be approximately 11 weeks. Subjects will be randomly assigned treatment as described in Section 2.3.

Subjects will be asked to treat their next migraine attack within 4 hours of onset provided that the headache severity is documented as being of mild, moderate, or severe intensity at that time and not improving. Subjects will record their response to the first dose over the next 48 hours using an electronic diary (e-diary). Subjects will be asked not to use rescue medication until at least 2 hours after dosing with study drug and completing the 2 hour assessments. If the migraine does not respond at 2 hours, a second dose of study drug may be taken up to 24 hours after the first dose as long as no other rescue medication has been used. If the migraine does respond within 2 hours (headache becomes pain-free) but then recurs after 2 hours a second dose of study drug may be taken up to 24 hours after the first dose. Subjects will record their response to a second dose, taken for either rescue or recurrence, for 48 hours in the e-diary. The total time for recording response to study drug is up to 72 hours depending on whether or not a second dose is used. Subjects are to contact the clinic to schedule EoS/Visit 2 within one week (7 days) after one attack has been treated, or after 8 weeks have passed without treating an attack. The total time on study is approximately 11 weeks.

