4.1 Subpopulations

The Safety-2nd Dose and ITT-2nd Dose populations will be further classified as rescue or recurrence populations. Subjects who took a second dose will be classified as either rescue or recurrence as follows:

- **Rescue:** subjects who did not achieve headache pain-free at 2 hours, completed the 2-hour assessments, and took a second dose of study drug between 2 hours and 24 hours post first dose.
- **Recurrence:** subjects who achieved headache pain-free at 2 hours, but then experienced recurrence of mild, moderate, or severe migraine pain and took a second dose of study drug up to 24 hours from the first dose.

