11.2 Primary Efficacy Analysis

The primary efficacy analysis will test the treatment effect, between lasmiditan 200 mg and placebo, of the primary efficacy endpoint of the proportion of subject's headache pain-free at 2 hours post-dose. This analysis will be presented by treatment group, based on the first dose.

Headache pain-free is defined as a reduction in headache severity from mild (1), moderate (2), or severe (3) at baseline to none (0).

Subjects who do not provide a headache pain severity rating at baseline, or who do not provide a headache pain severity rating at the two-hour time point will be assumed to have not achieved headache pain-free.

Subjects taking any rescue medication within the first two hours will be assumed to have not achieved headache pain-free. Subjects who use other medication prior to the study drug to treat the migraine attack will also be assumed to have not achieved headache pain-free.

Subjects who treat a no (0) severity migraine will not be included in the primary analysis. Sensitivity analyses, as described in Sections 11.4, 11.5 and 11.6 will also be performed for the primary endpoint on the mITT population.

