11.7.13 Headache Pain-Free After Second Dose

Counts and percentages of the number of subjects who are headache pain-free after second dose will be presented at the 0.5, 1, 2, 4, 24, and 48-hour post second dose time points. This summary will be presented by treatment sequence for the ITT-2nd Dose population, and separately for subjects taking a second dose for rescue or recurrence.

Headache pain-free after second dose is defined as experiencing a mild (1), moderate (2) or severe (3) headache at second-dose baseline which becomes none (0) at the summarized time point after a second dose is taken.

Subjects missing a headache severity at baseline or at the summarized time point will not be summarized at that time point.

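### The SAP's exploratory second-dose analyses have no rule for other acute migraine medication, and SAP 5.1 does not say what became of the exclusion in protocol 10.6.1

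*Protocol*

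**What the plan says.** **Protocol.** Section 7.3.1 allows a subject who is not pain-free at 2 hours a second dose that "may be taken up to 24 hours after the first dose as long as no other rescue medication has been used". Section 10.6.1 adds an analysis rule for rescue: "Subjects that use an alternative rescue medication will not be included in the summary statistics of response to treatment for rescue". Section 10.3.2 also defines a supportive per-protocol second-dose population, which admits subjects "if they use a second dose for rescue or recurrence of a migraine attack and do not deviate from the protocol". For recurrence, section 7.3.2 says only that if the headache clears "but then recurs after 2 hours, a second dose of randomized study drug may be taken up to 24 hours after the first dose". Neither 7.3.2 nor 10.6.2 sets a condition on other medication.

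**SAP.** The conduct condition appears in the study summary (2.1: "as long as no other rescue medication has been used") but not as a rule for the second-dose analyses. The ITT-2nd Dose population (4) sets no such condition. The Rescue subpopulation (4.1) takes subjects who were not pain-free at 2 hours, "completed the 2-hour assessments, and took a second dose of study drug between 2 hours and 24 hours post first dose". Section 5.2 gives second-dose data a starting point but no cut-off at other medication. Pain-free after the second dose (11.7.13) means a headache that "becomes none (0) at the summarized time point after a second dose is taken", tabulated to 48 hours. Relief, MBS-free and the Kaplan-Meier endpoints (11.7.14 to 11.7.18) follow the same pattern. Section 5.1 removes the mITT-2nd Dose and PP-2nd Dose populations and gives a reason. It does not mention 10.6.1.

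**The concern.** The protocol limited the mixing of second-dose response with response to other drugs in two ways: the exclusion in 10.6.1 and the supportive per-protocol set. The SAP removes the second openly and omits the first without comment. Protocol section 10 says that changes to the analysis methods, with their justification, will be described in the SAP, so the omission should have been recorded there.

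A subject who takes an analgesic before the second dose, or some hours after it, and then reports no pain is a responder under 11.7.13 and an event under 11.7.14 if this happens within 24 hours. The effect of the second dose is a stated objective (protocol 5.3), and protocol 4.5 ties it to establishing the dosing profile. SAP section 11 also plans logistic regression for second-dose endpoints, with the Firth method as a fallback. Both the response rates by sequence and the comparison of active with placebo second dose within a lasmiditan arm are exposed.

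**Working it through.** The plan states no figure on this point, so there is none to reproduce. The check is a comparison of texts, followed by an illustration.

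**Step 1. Where is other medication dealt with?**

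| Item | Protocol | SAP |
|---|---|---|
| Condition for taking a rescue second dose | 7.3.1, yes | 2.1, restated as conduct only |
| Rescue set definition | 10.3.2, no condition | 4.1, no condition |
| Exclusion from the rescue response summary | 10.6.1, yes | none |
| Per-protocol second-dose set | 10.3.2, yes | removed in 5.1 |
| Non-response or censoring for use after the second dose | none | none in 11.7.13 to 11.7.18 |
| Recurrence: any exclusion from the response summary | none in 10.6.2 | none |

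The Rescue definition in SAP 4.1 is therefore not itself a departure, because the protocol's definition also lacks the condition. What is lost is the rule that sat on top of it in 10.6.1.

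**Step 2. Are such rules used elsewhere in the SAP?** For the primary endpoint they are: "Subjects taking any rescue medication within the first two hours will be assumed to have not achieved headache pain-free" (11.2), and medication taken before study drug for the same attack is also a failure. Section 11.3 does the same for MBS. Sustained pain-free (11.7.2) requires that nothing else was taken after the first dose.

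**Step 3. Illustration.** All rates are assumed. Let u be the share of second-dose takers in a sequence who use another drug, and g the gain in response probability that it brings. Then:

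- inflation of a sequence's response rate = u × g
- shift in the active-minus-placebo difference = (u_active − u_placebo) × g, with the same g in both

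| u_active / u_placebo | g | Active inflated by | Placebo inflated by | Shift in difference |
|---|---|---|---|---|
| 5% / 10% | 10 points | 0.5 | 1.0 | −0.5 |
| 10% / 20% | 20 points | 2.0 | 4.0 | −2.0 |
| 15% / 30% | 30 points | 4.5 | 9.0 | −4.5 |
| 20% / 20% | 10 to 30 points | 2.0 to 6.0 | 2.0 to 6.0 | 0 |
| 30% / 15% | 30 points | 9.0 | 4.5 | +4.5 |

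**Step 4. Deletion compared with counting as failure.** Take use after the second dose only. Let t be response without the other drug, u the share of failures who use it, and r the share of those who then become pain-free.

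- SAP as written: t + (1 − t) × u × r
- Deleting all users, as 10.6.1 literally reads: t / [1 − (1 − t) × u]
- Counting users as failures: t

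With t = 0.45 v 0.35, u = 0.30 v 0.45, r = 0.60:

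- SAP: 0.45 + 0.55 × 0.30 × 0.60 = 0.549; 0.35 + 0.65 × 0.45 × 0.60 = 0.5255; difference 0.0235
- Deletion: 0.45 / 0.835 = 0.539; 0.35 / 0.7075 = 0.495; difference 0.044
- Failure: 0.45 v 0.35; difference 0.10

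With milder inputs (u = 0.20 v 0.30, r = 0.40) the SAP gives 0.494 v 0.428, a difference of 0.066. Deletion also distorts the result, because it removes failures who later needed something else. Restoring 10.6.1 word for word is therefore not the best repair.

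**The case against.** **The SAP does not say that these subjects are included.** It describes itself as specifying the protocol's methods, so a rule that it does not repeat could be taken as still in force. A reader might infer a deliberate decision to admit them; the text does not show one. But the second-dose sections are written out in full, and anyone programming from them would apply no exclusion.

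**10.6.1 may mean something narrower.** Elsewhere in the protocol, alternative rescue is the option other than a second dose. The sentence could then cover only subjects who took something else instead, and they are outside the second-dose set anyway. Against that, the sentence would be redundant, although 10.6.2 contains a similarly redundant statement. The ambiguity stands. It does not remove the gap: 7.3.1 makes prior use a departure from the conduct rule, and no second-dose efficacy definition deals with it.

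**The SAP does report other medication.** Section 8.5 tabulates it by sequence for ITT-2nd Dose, so it would be wrong to say that use goes unseen. But the categories are before and after the 2-hour assessment, not before and after the second dose, and the table does not alter any response count.

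**The comparison with 11.2 is uneven.** That section governs a confirmatory endpoint. Most first-dose exploratory endpoints also have no failure rule for non-study medication. This is fair, and it lowers the weight of the point.

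**Recurrence.** A reader might extend the conflict to recurrence. The documents do not support that, because the protocol has no recurrence exclusion for the SAP to drop.

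**Conclusion.** The point holds for the exploratory rescue second-dose analyses. Protocol 10.6.1, on its plain wording, and the SAP need to be reconciled, and the SAP as written credits the second dose with relief that followed another drug. For recurrence, the same rule would be an improvement for consistency, not the repair of a contradiction. The primary and key secondary tests and their error rate are untouched.

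The size is unknown. With the assumed inputs of Step 3, response rates are inflated by 0.5 to 9.0 points and the contrast shifts by anything from −4.5 to +4.5 points, with no shift when use and gain are equal. It is tempting to conclude that the contrast must shrink because subjects given placebo need more additional medication. That is plausible, but the documents give no usage rates and it remains an assumption. The fall from 10 to about 2.4 points in Step 4 likewise rests on chosen inputs, and it treats response without other medication as the quantity of interest.

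**What to change.** In SAP 5.1, state how protocol 10.6.1 is handled and why. In 11.7.13 to 11.7.18, and in 11.7.19 where it uses the second dose, add two rules for rescue and, for consistency, for recurrence:

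1. Leave out of the second-dose efficacy summaries any subject who recorded other acute migraine medication between the first and second dose. This is settled before the second dose is taken, so the exclusion cannot depend on which second dose was received.
2. Keep subjects who record such medication after the second dose, but count them as non-responders from that time and as non-events in the Kaplan-Meier analyses. Do not delete them.

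Timing should come from the timed diary rescue entries (protocol 9.1.8.1 and 10.5.1). The diary question described in SAP 11.7.10 covers the whole period since the migraine began, and SAP 4.2 notes that CRF medications carry start dates without times. Where the diary cannot place the use before or after the second dose, state a default and show the result without those subjects.

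The cost is SAP wording, a little more programming and somewhat lower reported second-dose response rates. No new data are needed and no treatment rule changes.
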